9.2 Sample Size Calculation

9.2.1 Total sample size

164 subjects are planned to be enrolled in this clinical trial. The sample size determination process is as follows:

This clinical study is a parallel positive control clinical validation design. The "anastomosis success rate" is adopted as the basis for sample size estimation. Based on literature review [3-11], the success rate of anastomosis is up to 100% when the similar devices are used for total laparoscopic distal gastrectomy for gastric cancer. According to relevant literatures and considering clinical practice, when such products are used for anastomosis from esophageal site to gastrointestinal site, the "success rate of anastomosis" can reach 97%. Therefore, the "anastomosis success rate" of this clinical trial is determined to be 97% with a clinical non-inferiority margin of 10%. The parameters are set as follows: $\alpha = 0.025$ (one-sided), $\beta = 0.2$, $\delta = 10\%$, and the ratio of test control group is 1:1. The estimation formula of sample size for non-inferiority clinical validation is adopted, and the sample size required in each group is at least 65 cases. The calculation formula [12] and correction formula [13] are as follows:

$$\begin{split} n_{A} &= \frac{(\pi_{A}(1-\pi_{A}) + \pi_{B}(1-\pi_{B}))(Z_{1-\beta} + Z_{1-\alpha})^{2}}{((\pi_{A} - \pi_{B}) - d)^{2}} \\ n_{B} &= \frac{n_{3} \left\{ 1 + \left[1 + 4/(\delta n_{A}) \right]^{\frac{1}{2}} \right\}^{2}}{4} \end{split}$$

Considering that the number of subjects who may drop out or be lost to follow-up during clinical validation is about 20%, the sample size of each group is expanded to 82 cases, and the total sample size required for the two groups is 164 cases.

9.2.2 Number of cases for clinical trial of each disease and reasons for determination

The investigational product is mainly used for the cutting and anastomosis of gastrointestinal tissues, other diseases therefore are not involved in this clinical trial.

9.2.3 Minimum and maximum number of subjects in each clinical trial institution and reason

A total of 164 subjects are planned to be enrolled in this clinical trial, and a total of 5 clinical trial institutions are planned to participate in this trial. In the trial, the sample balance in each site should be maintained as far as possible. In combination with the total sample size and the number of participating clinical trial institutions, considering different number of disease sources in each center and possible difficulties in individual centers, each clinical trial institution should recruit at least 16 subjects but no more than 60 subjects.

9.3 Significance Level and Power of Clinical Trial

Significance level α (one-sided) = 0.025 with 80% power.

9.4 Expected Dropout Rate

A 20% dropout rate is expected during sample size estimation.

This drop-out rate refers to the proportion of subjects who finally can not be included in the primary analysis. Drop-out subjects refer to those confirmed by the principal investigator with serious protocol violation (affecting the main evaluation/efficacy evaluation). The following conditions may be included, but not limited to: the subject violates the inclusion and exclusion criteria; the subject does not receive any examination/treatment with the study device; the subject receives the concomitant medication/device prohibited by the protocol; the data of main evaluation indicators are missing; the subject fails to obtain any data after randomization; the subject fails to complete the follow-up visit according to the regulations.

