8.2.3 Randomization

The trial was stratified by clinical trial institutes with the randomization method of stratified blocks. The seed number and block length were determined with SAS9.1 statistical software programming. The subjects were divided into the test group and the control group in a ratio of 1:1. The random grouping arrangement of at least 164 subjects was generated, and the corresponding sequentially numbered, opaque and sealed randomization envelopes were made. The randomization envelopes were kept and allocated by relevant personnel who were not involved in the screening and treatment of subjects and authorized by the investigator.

The random number is a 4-digit sequential number consisting of "center number" and "serial number" (which is generally the "center digit occupied + sample size digit occupied"). The first digit is the number of the clinical trial institution, and the last 3 digits are the "serial number" assigned by randomization. When the serial number is less than 3 digits, add "0" to make up 3 digits. If the randomization number "1001" is the first randomization number of the clinical trial institute with the institute number of 01, it corresponds to the first subject randomized at the institute.

When a subject was determined to be enrolled, the investigators or other authorized designee requested randomization assignment from the randomization envelope manager. The randomization envelope keeper took out the randomization envelope in the order of random number, filled in the screening number and initials of the subject to be assigned to the designated place on the back of the envelope, and signed the name and date to complete the allocation. The investigators or other authorized designee then intervened based on the results of the randomization assignment (i.e., test groups).

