9.7.1 Statistical method for data

Statistical analysis is performed using the SAS 9.1 software.

Statistical description on all data, including demographic data, baseline data, all efficacy indicators and all safety data shall be performed. Measurement data will be statistically described using mean, standard deviation, minimum, maximum, median, 25th percentile and 75th percentile; enumeration data will be statistically described using frequency and percentage.

The primary effectiveness evaluation indicator (anastomosis success rate) is evaluated by the confidence interval method.

The secondary evaluation indicators are evaluated by the difference test. Measurement data are compared using two independent samples t-test or Wilcoxon rank sum test. Enumeration data are compared using Pearson's X^2 test or Fisher's exact test.

The safety evaluation indicators are evaluated by the difference test. Enumeration data are compared using Pearson's X^2 test or Fisher's exact test. The adverse events and device defects occur in this trial shall be shown in list.

The stapler operational performance is evaluated by the difference test. Enumeration data are compared using Pearson's X^2 test or Fisher's exact test.

The central effect is considered in the analysis process. The general linear model is used for measurement data, and CMH or logistic regression is used for enumeration data.

9.7.2 Missing, unused, or incorrect data (including dropouts and withdrawals) and unreasonable data

All missing, unused or incorrect data (including dropouts and withdrawals) and unreasonable data will be discussed and finally determined by the investigators and biostatistician in the data review stage. The basic statistical principles for the processing of these data are as follows:

- (1) The details of each drop-out case shall be described, and the drop-out between the test group and the control group shall be compared using Pearson X^2 test or Fisher exact test;
- (2) Missing data at baseline shall not be estimated;
- (3) Missing values of main evaluation indicator (success rate of anastomosis) shall not be estimated;

Clinical Trial on Performance and Safety of Disposable Powered Articulating Endoscopic Linear Cutter Stapler in Gastrointestinal Tissue Cutting and Anastomosis

- (4) Missing values of secondary evaluation indicators shall not be estimated;
- (5) Missing values for operational performance evaluation shall not estimated;

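### Exclusions from the primary analysis rest on an open-ended list, by a review not stated to be blind to arm or outcome, and the plan does not say which analysis set decides; near the boundary one removal can change the verdict.

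*Combined protocol and SAP*

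**What the plan says.** **Who leaves the primary analysis.** Section 9.4 equates its drop-out rate with the share of subjects who cannot enter the primary analysis. It then says: "Drop-out subjects refer to those confirmed by the principal investigator with serious protocol violation (affecting the main evaluation/efficacy evaluation"). The reasons are introduced by "The following conditions may be included, but not limited to". They include failure to complete follow-up.

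**When the outcome is known, and to whom.** Section 8.1.15.1 scores anastomosis success during surgery. Sections 8.1.3(4) and 8.2.4 say that investigators know the allocation and only subjects are blinded.

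**Who else is involved.** Section 9.7.2 has the investigators and the biostatistician settle missing, drop-out and withdrawal data at data review. Section 10.4 requires the analysis sets to be settled before lock. Neither mentions blinding.

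**Which set decides.** Section 9.9 names the PPS as the primary efficacy population. In the preceding item it names the FAS as primary for baseline data and, in parentheses, for efficacy evaluation. Section 9.5 sets the success rule without naming a set.

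**Missing outcomes.** Section 9.7.2, item 3: "Missing values of main evaluation indicator (success rate of anastomosis) shall not be estimated". Items 7 and 8 give worst-case estimation and sensitivity analysis to safety measures only. Item 1 requires every drop-out to be described and the arms to be compared on drop-out.

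**The concern.** The primary endpoint is complete when the operation ends. Any later decision to exclude is therefore made when the outcome can be known, by a process that includes people who know the arm, on grounds that can be added to.

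This does not need bad faith. Section 8.1.12(2)c makes an SAE a reason for withdrawal, and section 8.1.16(6) treats adverse events related to the anastomosis as SAEs. A withdrawn subject does not complete follow-up, and incomplete follow-up is a listed ground in 9.4. Followed as written, these rules can take an observed device failure out of the PPS.

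Non-inferiority is the sensitive setting for this. With an expected success rate of 97% there are only two or three failures per arm (82 × 0.03 = 2.5), so the verdict turns on single subjects. The sample size allows 82 − 65 = 17 exclusions per arm.

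**Working it through.** **Inputs.** One-sided alpha and power: "Significance level α (one-sided) = 0.025 with 80% power" (9.3). Rate and margin: the success rate "of this clinical trial is determined to be 97% with a clinical non-inferiority margin of 10"% (9.2.1). Allocation: "The subjects were divided into the test group and the control group in a ratio of 1:1" (8.2.3). Evaluable number: "the sample size required in each group is at least 65 cases" (9.2.1). Allowance: "A 20% dropout rate is expected during sample size estimation" (9.4). Success rule: lower 95% limit of test minus control above -10% (9.5). Section 9.7.1 names no interval method, so several are shown. The true rates of 87% and 93% in the test arm are my assumptions.

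**The plan's own figure.**
- n = [2 × 0.97 × 0.03 × (0.8416 + 1.9600)²] / 0.10² = 45.68.
- Correction: (45.68/4) × [1 + √(1 + 4/(0.10 × 45.68))]² = 64.1, rounded up to 65.
- Drop-out: 65/0.80 = 81.25, rounded up to 82 per arm, 164 in total.

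The plan's figures are reproduced.

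**Effect of one removal, 82 per arm, 2 control failures.** Only failed test-arm subjects are removed. The Wald limit is p_T − p_C − 1.96 × √[p_T(1−p_T)/n_T + p_C(1−p_C)/n_C].
- 6 v 2 failures: 0.9268 − 0.9756 − 1.96 × 0.03343 = -11.43% (fail).
- One test failure removed, 76/81 v 80/82: 0.9383 − 0.9756 − 1.96 × 0.03171 = -9.95% (pass).

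| Method | Failures, test v control | All 82 per arm | One test failure removed |
|---|---|---|---|
| Wald | 6 v 2 | -11.43% | -9.95% |
| Newcombe | 5 v 2 | -11.26% | -9.80% |
| Miettinen-Nurminen | 5 v 2 | -11.42% | -9.94% |

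**Chance of declaring non-inferiority.** Exact binomial enumeration, 82 per arm, control rate 97%, with up to 0, 1 or 2 failed test subjects removed in every trial:

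| True test rate | Method | 0 | 1 | 2 |
|---|---|---|---|---|
| 87% (at the margin) | Miettinen-Nurminen | 2.1% | 4.3% | 7.5% |
| 87% | Newcombe | 2.1% | 4.7% | 8.6% |
| 87% | Wald | 4.3% | 8.7% | 12.5% |
| 93% | Miettinen-Nurminen | 32% | 47% | 58% |

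**Restoring the allowed exclusions.** Suppose 65 per arm are analysed with 2 failures in each. The Miettinen-Nurminen limit is -7.9% (pass). Restore the 17 excluded per arm and let all excluded controls be successes. The result becomes a fail once 3 of the 17 test subjects are failures (5 v 2, -11.4%). By Wald it takes 4 (6 v 2, -11.4%).

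**The case against.** Four stronger readings are tempting, and the documents do not support them.

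- **That the principal investigator alone decides.** Section 9.4 sits under the drop-out allowance. Section 9.7.2 adds the biostatistician and 10.4 has the sets settled before lock. What remains is that none of these sections states blinding, and they are not reconciled with each other.
- **That nothing in the plan would reveal selective exclusion.** The FAS has no compliance filter, so it would keep a treated subject with an observed failure. An FAS analysis of the 5 v 2 example gives 77/82 v 80/82, a Miettinen-Nurminen fail. Item 1 of 9.7.2 also discloses each drop-out, though a test comparing drop-out between arms will not detect one or two. The gap is that the plan does not say what follows if the FAS and PPS disagree, and the FAS does not recover missing outcomes.
- **That item 3 of 9.7.2 discards observed outcomes of excluded subjects.** It covers missing values only. Removal of observed outcomes comes from 9.4 and the PPS definition.
- **That any exclusion can reverse the result.** It takes a result near the boundary and removal of test-arm failures. The interval method also matters: by Wald, 5 v 2 already passes at -9.82%, and the reversal appears at 6 v 2.

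It is also fair to say that section 9.1 defers detail to an SAP finalised before lock, which could add rules. Lock comes after every outcome is known, so that is late for fixing exclusion grounds.

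**Conclusion.** The concern holds in a limited form. The rules as written can remove an observed intraoperative failure from the PPS, on grounds that are not closed, through a review not stated to be blind. The plan names two primary efficacy sets with no rule for disagreement, and leaves missing primary outcomes without a sensitivity analysis.

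The sizes are worst cases: only test-arm failures are removed, and a reversal needs a result close to -10%. Under those assumptions one removal moves the lower limit by about 1.5 percentage points and roughly doubles the false-claim rate at the margin (2.1% to 4.3% by Miettinen-Nurminen). If both arms are truly 97%, one removal changes the verdict in about 3% (Wald) to 8% (Newcombe, Miettinen-Nurminen) of trials. This should be corrected before enrolment. It is not evidence that exclusions would in fact be selective.

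**What to change.** 1. Replace the list in 9.4 with a closed list fixed before the first subject is enrolled. Remove incomplete follow-up as a ground for excluding an outcome already observed in surgery.
2. Have data management and the biostatistician classify subjects before lock, from listings that show neither arm nor primary outcome.
3. Reconcile 9.4, 9.7.2 and 9.9, and state in 9.5 that non-inferiority must hold in both the FAS and the PPS.
4. Add, as a sensitivity analysis and not as the main analysis, one that counts operated subjects with no recorded outcome as non-successes, with a tipping-point table over excluded and missing outcomes.
5. Reconcile 8.1.12(2)c and 8.1.16(6) with 9.4, so that it is clear how a subject withdrawn after an anastomosis-related event is handled in the primary analysis.

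Cost: protocol and SAP wording, one table and a little more analysis, with no extra subjects or visits. The downside is a stricter success requirement when the two sets differ.

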9.5 Qualification/Disqualification Criteria for Clinical Trial Results

The non-inferiority hypothesis is tenable if the lower limit of 95% confidence interval of the difference in the primary effectiveness evaluation indicator between the test group and the control group is greater than the non-inferiority critical value (-10%).

The secondary effectiveness evaluation indicators and safety evaluation indicators are tested by difference test, and the significance level is set at 0.05. If the test result of the difference in any secondary evaluation indicator and safety evaluation indicator between the test group and the control group is p > 0.05, then there is no significant difference in this indicator between the test group and the control group.

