14.1.5 Handing protocol of adverse events that may occur in this clinical trial

- (1) Anastomotic bleeding: It is related to the factors of anastomotic leakage. The bleeding is generally the technical factor. The prevention is mainly to avoid the tension at the anastomotic stoma and the fat drop left at the cutting site.
- (2) Anastomotic leakage: The incidence of anastomotic leakage is reported to be 4% to 15% in the literature. It may be caused by the stapler, or related to the patient's condition or the doctor's operation;
- (3) Anastomotic stricture: It is one of the most common complications, mostly occurring after 1 month after surgery.
- (4) Major incisional bleeding: Drop in hemoglobin $\geq 20g/l$ resulting in ≥ 1 transfusion.
- (5) Minor incision bleeding: Bleeding that does not meet the criteria for "severe bleeding".
- (6) Incision site infection: Infection at the incision site due to improper nursing, resulting in prolonged incision healing time, prolonged suture removal time, or unplanned antibiotic therapy.
- (7) Delayed healing of incision: The incision in contact with suture has delayed healing time.
- (8) Anemia and hypoproteinemia: Symptoms caused by tumor deterioration in patients with gastric cancer;
- (9) Tumor recurrence or metastasis: Symptoms caused by further tumor deterioration in patients with gastric cancer;

(10) Gastrointestinal discomfort symptoms: Common symptoms of gastrointestinal diseases, such as nausea, belching, constipation, diarrhea, acid reflux, abdominal pain, etc.

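### Section 9.5 judges safety indicators only by whether p exceeds 0.05, with no between-arm difference or interval, in a trial not adequately powered to detect a doubling of anastomotic leakage

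*Combined protocol and SAP*

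**What the plan says.** Section 9.5 sets out the criteria for judging the trial's results. The primary endpoint has a margin and an interval rule: the lower 95% limit for the difference in success rate must lie above -10%. Secondary and safety indicators have neither. They are tested for a difference at 0.05, and when the result "is p > 0.05, then there is no significant difference in this indicator between the test group and the control group", that is the finding.

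Section 9.7.1 repeats the split. The primary endpoint is assessed by a confidence interval, whereas "The safety evaluation indicators are evaluated by the difference test", using Pearson's chi-square or Fisher's exact test for counts. No rule is given for choosing between the two tests.

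The sample size and the statement "Significance level α (one-sided) = 0.025 with 80% power" (Section 9.3) rest on anastomosis success alone, which is scored during surgery (Section 8.1.15.1). Leakage is assessed from the end of surgery to the end of follow-up (Section 8.1.16). The one leakage rate in the documents is in Section 14.1.5: "The incidence of anastomotic leakage is reported to be 4% to 15% in the literature".

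Section 3.1 gives comparison of effectiveness and safety, for a registration application, as the trial's purpose. Section 8.1.2 makes differences in the safety indicators a secondary objective.

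**The concern.** A non-significant test tells the reader something only if the trial had a reasonable chance of a significant one. Here the sample size was fixed on a different endpoint, and the criteria attach no estimate of uncertainty and no caveat to a non-significant safety result. When events are few, p > 0.05 is easy to obtain whether or not the arms differ.

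What is at stake is the safety half of the trial's purpose. A report could follow Section 9.5 to the letter and say that leakage did not differ significantly, while the same data remained compatible with a large excess in the test arm. The planned text would not tell the reader how large an excess had been ruled out.

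**Working it through.** **1. Inputs.** Section 9.2.1: an expected success rate that "of this clinical trial is determined to be 97% with a clinical non-inferiority margin of 10" per cent; "the ratio of test control group is 1:1"; "the sample size required in each group is at least 65 cases"; and, after 20% dropout, "the sample size of each group is expanded to 82 cases". Section 9.5: level 0.05 for safety tests, sidedness not stated and taken as two-sided. Section 14.1.5: leakage 4% to 15%, midpoint 9.5%.

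**2. The plan's own figure.** n = 2 × 0.97 × 0.03 × (1.960 + 0.842)² / 0.10² = 45.7, rounded up to 46. The correction (n/4) × [1 + √(1 + 4/(0.10n))]² gives 64.1 from 45.7, or 64.4 from 46, so 65. Then 65/0.8 = 81.25, so 82 per arm and 164 in total. This matches Section 9.2.1, so the primary calculation is not in question.

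**3. Power for a doubling of leakage.** For control rate p and test rate 2p, power is the sum over all (i, j) of Bin(i; n, p) × Bin(j; n, 2p), counting the pairs for which the test rejects at 0.05. Both permitted tests were enumerated. The sample size for 80% power uses the normal approximation for two proportions.

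| Control v test rate | Fisher, n = 82 | Pearson, n = 82 | Fisher / Pearson, n = 65 | n per arm for 80% power |
|---|---|---|---|---|
| 4% v 8% | 10% | 17% | 7% / 15% | 553 |
| 9.5% v 19% | 34% | 41% | 26% / 34% | 212 |
| 15% v 30% | 57% | 64% | 46% / 54% | 121 |

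The chance that a true doubling gives p > 0.05 with 82 per arm is one minus these values: 83% to 90% at a 4% control rate, 59% to 66% at 9.5%, and 36% to 43% at 15%.

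**4. A larger contrast.** For 15% against 4%, the two ends of the protocol's own range, exact power with 82 per arm is 61% (Fisher) or 70% (Pearson). By normal approximation, the test-arm rate detectable with 80% power is about 17.4% against a 4% control rate, and about 33.6% against 15%.

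**5. What particular results would look like (82 per arm).**
- *8 leaks v 2.* The rates are 9.8% and 2.4%, a difference of 6/82 = 7.3 points. The pooled rate is 10/164 = 0.0610, so z = 0.0732 / √(2 × 0.0610 × 0.9390 / 82) = 1.958 and Pearson p = 0.0502. Fisher p = 0.099. The Miettinen-Nurminen 95% interval is -0.04 to +16.0 points. Under Section 9.5 both tests return no significant difference.
- *3 leaks v 3.* The rates are 3.7% each and the interval is -7.1 to +7.1 points. Identical counts still leave open an excess of up to 7.1 points over an observed 3.7%.
- *Against 3 control leaks,* significance needs 10 test-arm leaks by Pearson or 11 by Fisher.

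**The case against.** The strongest reply is that Section 9.5 only states the ordinary meaning of a non-significant test. A reader might infer from the section's heading that p > 0.05 certifies the device as comparable or safe. The documents do not say so. The one success threshold in Section 9.5 belongs to the primary endpoint, and Section 8.1.2 asks whether safety differences exist, not for proof that they do not. This stands. The defect is what is left out after a non-significant result, not a false claim.

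A reader might also infer that the trial cannot detect a doubling of leakage, or that real harm is certain to be missed. That is too strong. At a 15% control rate a doubling is detected more often than not by either test.

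Nor do the figures extend to every indicator. They are for leakage only, and the documents give no bleeding or SAE rate. Section 8.1.16 counts anastomosis-related adverse events as serious, so SAEs may be more frequent than any single complication. Most secondary indicators are measurements, for which 82 per arm gives 80% power for about 2.80 × √(2/82) = 0.44 standard deviations. No shortfall has been shown for them.

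There are safeguards. Section 9.7.1 requires frequencies and percentages for all safety data and lists adverse events and device defects, so an 8 v 2 split would be visible. Section 9.7.2 sets missing safety values to the worst case and asks for a sensitivity analysis on the safety set. The centre-effect models in Section 9.7.1 could yield between-arm estimates, although the text does not commit to reporting them. Section 9.1 leaves detail to an SAP finalised before lock, which could add intervals. None of these supplies a between-arm difference with its uncertainty. Under Section 9.8, analyses not pre-specified in the SAP count as exploratory, so the intervals have to be written in beforehand.

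Finally, low power for safety is usual when efficacy sets the sample size. That is so, and no more subjects are asked for.

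**Conclusion.** The point holds for safety indicators and should be fixed before database lock. Their only criterion in Section 9.5 is a difference test at 0.05, and the protocol names no between-arm difference or interval to accompany it. For a doubling of leakage, power with 82 per arm runs from 10% to 64% across the documents' 4% to 15% range, below the trial's 80% standard throughout. At the low end, a true doubling would probably be reported as no significant difference.

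This rests on a two-sided 0.05 test, control leakage within 4% to 15%, and all 82 per arm being evaluable for safety. The last is the favourable case. The 20% dropout in Section 9.4 is defined for the primary analysis, so the safety set may stay near 82; with 65 per arm, power falls to between 7% and 54%.

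The primary non-inferiority test, the sample size and the data collected are unaffected.

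**What to change.** Amend the second paragraph of Section 9.5, and carry the change into Section 9.7.1 and the SAP before database lock:

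- For each safety indicator, report the rate in each arm, the risk difference and its 95% confidence interval. Name the interval method; Miettinen-Nurminen suits sparse counts.
- Word the conclusion by what the upper limit excludes. For 8 v 2, that is an excess above about 16 points, and nothing smaller.
- State that p > 0.05 does not show comparable safety and is not a qualification criterion. P-values may stay as description.

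Reporting secondary indicators as a difference with a 95% interval would be consistent, but is optional.

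The cost is a wording change and one extra table column, with no effect on enrolment or conduct. The downside for the sponsor is a safety statement less favourable than a bare report of no significant difference.
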